5.2. Analysis method

Appropriate tests including χ^2 test are employed for analysis, depending on the analysis-data scale and the characteristics.

6. Presence/absence of analysis and its schedule

Analysis objective	The survey's reporting interval and the deadline	
	of re-examination	
The 6th periodical safety	January 1, 2016 to December 31, 2016	
report		
Re-examination	June 14, 2013 to May 15, 2017	
Final report	June 14, 2013 to March 31, 2018	

7. Softwares/dictionary used for analysis

7.1. Statistical analysis and listing softwares

The softwares and their versions for use are as follows:

	Software and version
OS	We use Microsoft Windows 7 or a more recent version.
Statistical analysis	We use SAS Ver. 9.2 or a more recent version.
software	
Listing software	We use Microsoft Excel 2010 or a more recent version.

7.2. Dictionary for use

The dictionaries used for the names of adverse events, complications, and drugs are as follows:

Item	Dictionary and its version	Remarks
Types of adverse events	Medical Dictionary for Regulatory	They are classified into a
and adverse	Activities / Japanese edition	System Organ Class (SOC) and
reactions/infections	(MedDRA/J 20.1)	the appropriate term among the
		preferred terms (PT) is selected
		for description.
		SOC is displayed in accordance
		with the international
		agreement.
		The MedDRA/J version used
		will be provided in a blank
		space.
Drug name (concomitant	Iyakuhinmei Data File (IDF) *An	• A 7-digit code is used, in
medication)	appropriate version should be used	principle, when concomitant
	for aggregation, depending on the	medications are counted per
	analysis period.	product.
		Give a priority to the lowest
		level codes when using codes
		for the list of concomitant
		medications (including
		Re-examination Attachment
		Form 3).

8. The definition of the groups used for analysis

Name of group	Definition
Registered patients	The patients assessed as eligible for registration
Patients whose survey	Registered patients whose survey form was locked.
form was locked	
Patients whose survey	Registered patients whose survey form was yet to be locked. See
form was yet to be	Reference Data "Survey form lock/unlock information" for the criteria
locked	for the status that a survey form is yet to be locked.
Patients excluded from	The patients whose survey form has been locked and who satisfy the
the safety analysis group	criteria of the patients excluded from the safety analysis group. See
	Reference Data "Inclusion/exclusion of patients" for the criteria to
	exclude patients from the safety analysis group.
	The exclusion items are as follows:
	Breach of contract: unsigned institutions/specialties
	Breach of contract: an excess of contracted number of patients
	Breach of contract: unsigned physicians
	Not treated with Humira
	Not confirmed by physician
	Overlapped patients
	Safety is not assessable
	Breach of registration criteria: a deviation from the registration period
	Breach of registration criteria: with a history of treatment with
	Humira
	Administration prior to contract
	Data credibility cannot be confirmed: closure/merger of medical
	institutions
	Data credibility cannot be confirmed: the physician was transferred
	Data credibility cannot be confirmed: the physician refuses
	confirmation
	Data credibility cannot be confirmed: inconsistency was found in the
	survey form
Patients in the safety	The remaining patients after the patients excluded from the safety
analysis group analysis group are removed from the patients whose survey fo	
	locked
Patients excluded from	The patients who satisfy the exclusion criteria for the effectiveness
the effectiveness analysis	analysis group. See Reference Data "Inclusion/exclusion of patients" for

Name of group	Definition	
group	the exclusion criteria for the effectiveness analysis group.	
	The exclusion items are as follows:	
	Breach of registration criteria: Not the disease to be surveyed	
	Effectiveness is not assessable	
Patients in the	The remaining patients after those excluded from the effectiveness	
effectiveness analysis	analysis group are removed from the patients in the safety analysis	
group	group.	

9. General agreement items for analysis

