9.1. Handling of missing data

No missing data at any time are imputed for analysis. Note that entry data need to be imputed in some items and the imputation method for imputation-required items is defined in the definitions of each item at Chapter 10 or thereafter.

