Calculate the number of target patients, the mean and standard deviation of partial Mayo score, the mean and standard deviation of changes in partial Mayo score for each assessment period, and conduct a paired-t test which compares the values at the initial administration.

In addition, calculate the mean of the mean days to the final assessment and the standard deviation.

Note: Follow "12.4 Assessment period for partial Mayo score" for Time Allowance of assessment period.

The analysis covers only the patients with the assessment applicable to Time Allowance of the first administration and each assessment period.

Multiplicity in the test will be adjusted by the Bonferroni method.

"3.1.5.1 Changes in the remission rate at each point of partial Mayo Score (Observed Case)"

Patients for analysis: patients in the effectiveness analysis group

Analysis objective: to show the remission rate of partial Mayo score per assessment period.

Analysis item: calculate the number of patients in the analysis groups.

Calculate the number of target patients, the percentage to the number of patients who achieved a remission and the number of target patients, 95%CI of the remission rate, and conduct a McNemar test for the first administration per assessment period.

In addition, prepare a line plot to describe the percentage to the target patients among the patients who achieved a remission per assessment period.

X-axis: assessment period (in week)

Y-axis: remission rate (%)

Note: Follow "12.4 Assessment period for partial Mayo score" for Time Allowance of assessment period.

The analysis covers only the patients with the assessment applicable to Time Allowance of the first administration and each assessment period.

For the confidence interval, use the Clopper-Pearson's confidence interval.

Refer to "10.3 Effectiveness analysis" for the calculation method and remission rate.

"3.1.5.2 Changes in the remission rate (NRI) at each point of partial Mayo Score"

Patients for analysis: patients in the effectiveness analysis group

Analysis objective: to show the remission rate of partial Mayo score per assessment period.

Analysis item: calculate the number of patients in the analysis groups.

Calculate the number of target patients, the percentage to the number of patients who achieved a remission and the number of target patients, 95%CI of the remission rate, and conduct a McNemar test for the first administration per assessment period.

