In addition, prepare a line plot to describe the percentage to the target patients among the patients who achieved a remission per assessment period.

X-axis: assessment period (in week)

Y-axis: remission rate (%)

Note: Follow "12.4 Assessment period for partial Mayo score" for Time Allowance of assessment period.

The analysis covers only the patients with the assessment applicable to Time Allowance of the first administration and each assessment period.

For the confidence interval, use the Clopper-Pearson's confidence interval.

Refer to "10.3 Effectiveness analysis" for the calculation method and remission rate.

NRI: when it is unknown whether the remission is achieved, impute the data without remission.

"3.1.7.1 Remission rate at Week 52 in patients who achieved a remission at Week 8 of administration based on partial Mayo score"

Patients for analysis: Patients in the effectiveness analysis group (the patients who did not achieve a remission when the administration was started but achieved the remission at Week 8 of administration in partial Mayo score)

Analysis objective: to show the remission rate of partial Mayo score at Week 52 of administration in patients in the analysis group.

Analysis items: calculate the number of target patients, the percentage to the number of patients who achieved a remission at Week 52 of administration and the target patients, and the confidence interval of the remission rate. (calculate them in both Observed Case and NRI patterns)

Note: the patients for analysis should have partial Mayo score at the first administration and Week 8 of administration and achieved a remission at Week 8 of administration except those who had already achieved a remission in partial Mayo score at the first administration.

Follow "12.4 Assessment period for partial Mayo score" for Time Allowance of assessment period.

For the confidence interval, use the Clopper-Pearson's confidence interval.

"3.1.7.2 Remission rate at Week 52 in patients who achieved the response as an index of partial Mayo score at Week 8 of administration"

Patients for analysis: Patients in the effectiveness analysis group (the patients who achieved a response at Week 8 of administration in partial Mayo score)

Analysis objective: to show the remission rate of partial Mayo score at Week 52 of administration in patients in the analysis group.

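### Patients excluded as not assessable for effectiveness never reach the non-responder imputation in SAP Table 3.1.5.2, so its remission rate is biased upward

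*SAP*

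**What the plan says.** SAP section 8 builds the effectiveness group by subtraction from the safety group. There are two exclusion items: the patient does not have the surveyed disease, or "Effectiveness is not assessable". For the detail of "the exclusion criteria for the effectiveness analysis group" the SAP points to separate Reference Data, which is not among the documents.

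SAP section 9.1 states the general rule, "No missing data at any time are imputed for analysis", and allows exceptions that are defined item by item. One such exception is the table titled "3.1.5.2 Changes in the remission rate (NRI) at each point of partial Mayo Score" (SAP section 13.3). Its population line reads "Patients for analysis: patients in the effectiveness analysis group". Its note ends with the imputation rule: "NRI: when it is unknown whether the remission is achieved, impute the data without remission". A few lines above, the same note says: "The analysis covers only the patients with the assessment applicable to Time Allowance of the first administration and each assessment period".

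Table 3.2 reports the physician's general improvement rate over the same effectiveness group. The case report form offers an unevaluable option for that judgement (protocol section 8(3), item 15), and SAP Table 1.4 displays a matching fourth category. The strata for this rate in SAP section 11 are only effective or better, and ineffective.

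**The concern.** NRI is meant to keep patients with an unknown outcome in the denominator and count them as failures. Whether effectiveness can be assessed is known only after treatment has started. If patients are removed on that ground first, some of those the rule is written for are gone before it is applied. No other table brings them back, because no NRI analysis on the safety group is planned.

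At stake is the meaning of the NRI rate. A reader would take it as the share of treated patients known to be in remission. As planned, it is that share among patients whose effectiveness was judged assessable. Table 3.2 has a similar gap, since patients excluded as not assessable are absent from its denominator.

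**Working it through.** **1. The plan's own figure.** SAP section 4.3, Table 1: 1500 enrolled, 70% dropout at Week 52, 30% of the remainder without a Mayo score, 30% remission among those scored.

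- At Week 52: 1500 × 0.30 = 450. With a score: 450 × 0.70 = 315.
- Half-width: 1.96 × √(0.30 × 0.70 / 315) = 0.0506, so 24.9% to 35.1%. This agrees with the SAP.
- Implied remitters: 0.30 × 315 = 94.5.

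**2. Order of operations.** Section 8 excludes first; Table 3.1.5.2 starts from what is left; imputation comes last.

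**3. Direction and size.** Let R be the NRI rate among all safety-group patients with the surveyed disease, e the share excluded as not assessable, and r the rate of known remission among those excluded. The table would report

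(R − e·r) / (1 − e).

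This exceeds R whenever r < R. If no excluded patient is a known remitter (r = 0), it equals R/(1 − e), so the factor is at most 1/(1 − e). The documents do not give e, so the values below are assumptions. The last column puts the 94.5 planning remitters over 1500 × (1 − e).

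| e | factor 1/(1 − e) | denominator | rate |
|---|---|---|---|
| 0 | 1.00 | 1500 | 6.3% |
| 5% | 1.05 | 1425 | 6.6% |
| 10% | 1.11 | 1350 | 7.0% |
| 20% | 1.25 | 1200 | 7.9% |

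For scale, the Clopper-Pearson interval for 94 of 1500 is 5.1% to 7.6%. The shift at e = 10% lies inside it; the shift at e = 20% goes past its upper limit.

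If excluded patients had known remission at half the overall rate (r = 3.15%), then at e = 10% the result would be (0.063 − 0.10 × 0.0315)/0.90 = 6.65%, not 7.0%.

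These rates are illustrative. They treat all 1500 as safety-group patients with the disease, count every unscored patient as a non-remitter, and borrow a full Mayo planning rate for a partial Mayo table.

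**4. The second restriction.** Read literally, the note keeps only patients with an assessment in the window at first administration and at each period. Little is then left to impute, perhaps only assessments with an incomplete sub-score, which SAP section 10.3 does not score. On the planning figures, a denominator of scored patients only gives 94.5/315 = 30.0%, which is the observed-case rate. Changing the population while leaving this sentence in place would remove the restored patients again.

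**5. Related tables.** Tables 3.1.7.1 and 3.1.7.2 also start from the effectiveness group, but both require partial Mayo scores at first administration and Week 8. A patient without those scores cannot enter whichever parent group is used, so these tables are little affected.

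**The case against.** The best reply is that the exclusion criterion cannot be seen. SAP section 8 gives a label and refers to Reference Data. Elsewhere a matching category belongs to the physician's overall judgement, made at Week 52 or at discontinuation. On that reading a patient who fails early can be recorded as ineffective and stay in the group, and a patient judged unevaluable may still have partial Mayo scores. This stands. It is why 1/(1 − e) is an upper bound, and why the fix should use existing scores.

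A reader might go further and infer any of the following. The documents do not support them.

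- That the 70% dropout measures the excluded share. It is the expected loss by Week 52. Discontinuation is not an exclusion item, and discontinued patients have their own assessment windows (SAP sections 12.3 to 12.5).
- That early treatment failures are the ones removed. The label does not say so.
- That a planned NRI rate of 30% would fall by several points. The 30% is the planned rate among the 315 scored patients. On the same figures the rate under full NRI is 6.3%, so the absolute shift at e = 10% is 0.7 points.
- That every NRI table is equally affected. Tables 3.1.7.1 and 3.1.7.2 are not.

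It is also fair to say that exclusions are disclosed by reason (Tables 1.1, 1.3 and 1.3.1), and that the tables described as showing a primary endpoint (3.4 and 3.4.1) do not specify NRI. Disclosure lets a reader work out a bound after the fact, but it does not correct the reported rate or show which excluded patients had scores. The supporting role of NRI lowers the priority without removing the defect.

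**Conclusion.** The point holds for Table 3.1.5.2. Followed as written, the plan never counts excluded patients with unknown remission status as non-remitters, and the NRI rate is too high by a factor of up to 1/(1 − e). The upward direction requires only that known remission be less common among excluded patients than in the full group. The size cannot be fixed from the documents: the assumed shares of 5%, 10% and 20% give factors of at most 1.05, 1.11 and 1.25.

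The sentence requiring an assessment at each period contradicts NRI in the same note and has to be corrected together with the group definition. Table 3.2 has a lesser form of the denominator problem. The change should be made, but the documents do not show that the bias is large.

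**What to change.** For Table 3.1.5.2:

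- Use as denominator all safety-group patients with the surveyed disease, including those classed as not assessable for effectiveness.
- Delete the requirement of an assessment at each post-baseline period.
- Use any partial Mayo score that exists in the window, and impute non-remission only where status is unknown.
- State how a missing score at first administration is handled, both for the rate and for the McNemar test, which needs a baseline status.

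In Table 3.2, add a second line on the same denominator that counts not assessable as not effective. Leave the observed-case tables as they are. Tables 3.1.7.1 and 3.1.7.2 need no change on this account.

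No new data are needed, because the exclusion reasons are already tabulated. The cost is a little extra programming and a slightly less favourable rate than NRI within the present group would give. Against the literal reading of the note the drop would be larger (30.0% to 6.3% on the planning figures), but nearly all of that comes from applying NRI at all.

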9.1. Handling of missing data

No missing data at any time are imputed for analysis. Note that entry data need to be imputed in some items and the imputation method for imputation-required items is defined in the definitions of each item at Chapter 10 or thereafter.

9.2. Descriptive statistics

The following will be calculated for categorial data and quantitative data.

Data type	Item to be calculated		
	Number of patients, percentage, etc.		
	When the percentage is calculated, the number of patients of		
Catanania 1 data	"unknown" and "not provided" is included in the denominator. Chapter		
Categorical data	13 stipulates the details regarding the setting of denominators.		
	The patients of "unknown" and "not provided" are excluded in the		
	statistical test.		
0 (1)	Number of patients, mean, standard deviation, median, minimal value,		
Quantitative data	maximal value, etc.		

9.3. Display digit for figures

The display digit for figures is as follows:

Type of figure	Display digit	
Mean, standard The figure in the significant digit + 2 digits of data is rounded of		
deviation, median	figure in the significant digit of data + 1 digit for display.	
Minimal value, maximal value	The same number of digits is used for the significant digit of data.	
Number of patients	Displayed as a whole number	
	The figure is rounded off to the nearest one decimal place for display.	
Percentage, 95%	When figures for Attachment Form 2, incidences of adverse events, etc are	
Confidence Interval	rounded off to two decimal places, the details are specified in the chart	
	layout.	
	Round the 5 decimal places down to the 4 decimal places.	
p value	When the figure is smaller than 0.0001, display it as <0.0001 across the	
	board.	
	The figure for duration of illness should be displayed with the significant	
	digit rounded to the one decimal place.	
Significant digit	For others, the display digit of data should be the significant digit.	
	As for CRP, the summary statistics except the number of patients should	
	be rounded off to two decimal places.	

9.4. Figure display rule

Case	Display rules
If a figure is	Hyphen "-"
incalculable	

9.5. Statistical test method

The test does not include the classification of unknown/not provided. In principle, the first layer is subjected to the intersegmental test of classified data. When adjusting multiplicity, describe it in each chart of Chapter 13.

9.6. Significant level

In principle, the significant level is 5%, two-tailed. p<0.05 (<5%) shall be considered significant.

10. Derivation and calculation methods for data

10.1. General

Data name	Derivation and calculation methods
	If the same code is found among the DCF codes of "[Humira
Number of site	UC]DCF code list_Company A" "[Humira UC]DCF code
	list_Company E", it should be regarded as 1 site.
Number of patients per	The number of patients are calculated per the identical DCF site
site	code.
Patients with an adverse	
event which occurred not	Patients with at least one adverse event which occurred not in the
in the safety analysis	safety analysis period
period	
Patients who developed	Patients with at least one event which is categorized into infection in
an infection	the "Priority Survey Item List_MedDRA20.1_FIX".
Patients who developed	Patients with at least one event which is categorized into tuberculosis
tuberculosis	in the "Priority Survey Item List_MedDRA20.1_FIX".
Patients who developed	Patients with at least one event which is categorized into malignant
malignant tumour	tumour in the "Priority Survey Item List_MedDRA20.1_FIX".
Patients who developed	Patients with at least one event which is categorized into
an administration site	administration site reaction in the "Priority Survey Item
reaction	List_MedDRA20.1_FIX".
Patients who developed	Patients with at least one event which is categorized into
an autoimmune disease	auto-immune disease in the "Priority Survey Item
an autominune disease	List_MedDRA20.1_FIX".
Patients who developed	Patients with at least one event which is categorized into
pancytopenia	pancytopenia in the "Priority Survey Item List_MedDRA20.1_FIX".
Patients who developed	Patients with at least one event which is categorized into
demyelinating disease	demyelinating disease in the "Priority Survey Item
demyelmating disease	List_MedDRA20.1_FIX".
Patients who developed	Patients with at least one event which is categorized into cardiac
cardiac failure	failure congestive in the "Priority Survey Item
congestive	List_MedDRA20.1_FIX".
Patients who developed	Patients with at least one event which is categorized into interstitial
interstitial pneumonia	pneumonia in the "Priority Survey Item List_MedDRA20.1_FIX".
Patients subject to AAA	Patients who are described in "UC Survey AAA Measurement (final
measurement	report)".

Data name	Derivation and calculation methods
	administration date. If the next record has already been generated and the first administration date of the next record comes earlier than the date imputed as the final date
	of the year, impute the first administration date of the next record - 1 day for the final administration date.
	Of note, if the final administration date is provided in the record where the final administration date of Humira has been identified according to the above rule and the "continued" checkbox is checked, follow the below:
	 If the described final administration date > the final administration date imputed according to the above rule, select the imputed final administration date as the final administration date of Humira for the patient. If the described final administration date <= the final administration date imputed according to the above rule, select the described final administration date as the final administration date of Humira for the patient.
	If the first administration date of Humira + 364 days < the final administration date of Humira imputed according to the above rule, select the first administration date of Humira + 364 days as the final administration date of Humira.
Days to the final administration date of Humira	The final administration date of Humira - the first administration date of Humira + 1
Administration status (dosage and administration)	Sort the data by the first administration date provided in "the administration status of Humira" in the survey form and aggregate the administration status (dosage and administration) according to the following rules: • If all the following [1] to [4] are satisfied, aggregate the data as "160mg→80mg→40mg once every two weeks and no changes thereafter". • If none of the following [1] to [4] is satisfied Aggregate as "others". [1] 1st administration: as a patient with a dose of 160mg

Data name	Derivation and calculation methods
	[2] 2nd administration: as a patient with a dose of 80mg
	[3] 3rd administration and thereafter: the dosing
	frequency "once every 2 weeks" is checked in the
	survey form, and a patient with a dose of 40mg
	* If the patient receives the third administration and
	thereafter, all the administration status should be the
	condition as shown in [3].
	[4] Patients who did not have a washout period for 30
	days or longer.
	If the administration status (dose and administration) is categorized
	in "others", follow the rules below to find the reason for the change
	in dose/dosing frequency.
	• 1st dose: "a reason for other than 160mg (a dose) or in the
	case of self-administration" in the survey form.
Reason for change in	• 2nd dose: "a reason for other than 80mg (a dose) or in the case
dose/dosing frequency	of self-administration" in the survey form.
	• 3rd and the subsequent dose(s): "a reason for other than 40mg
	(a dose), or in the case of other than once every 2 weeks
	(dosing frequency)" or "reason for change in dose/dosing
	frequency" in the survey form.
	Dosing frequency
	[1] Sort data in the order of "the first administration date" of "the
	administration status of Humira", dosing frequency and
	description.
	[2] Calculate the dosing interval per data on administration status
	The interval between first and second administrations should
Administration status	be 14 days.
	• For the third and subsequent dose(s), the interval should be 14
(total number of dosing,	days if the dosing frequency "once every 2 weeks" is checked
total dose)	while the dosing frequency should be obtained from "[Humira
	UC] Conversion data provided for analysis" if the dosing
	frequency is "others".
	[3] Calculate the dosing frequency per data on administration
	status.
	Dosing frequency = (the final administration date (after
	imputed) – the first administration date(after imputed))/dosing

Data name	Derivation and calculation methods
	frequency (number of days)
	[4] When the results of [3] are ">0" (bigger than 0) and "<1"
	(smaller than 1), the dosing frequency shall be counted as 1.
	If the figure is ">=1" (1 or bigger), round the decimal down to the
	integer for the dosing frequency.
	[5] The total number of dosing shall be the total of [4] per patient.
	• Dose
	[1] If "Others" of a Humira dose is checked, the dose should be
	obtained from "[Humira UC] Conversion data provided for
	analysis".
	[2] Calculate the dose per data of the administration status.
	Dose = the number of dosing * a dose
	[3] The total dose should be the total of [2] per patient.
	• The mean daily dose
	The mean daily dose = the total dose/the total number of dosing
	If a patient's final administration date of Humira comes before the
	first administration date of Humira + 336, we handle the patient as a
Discontinued patients	discontinued case.
	Follow the above definition, no matter whether the discontinuation is
	selected in the survey form.
	"Present" is defined for the situation where a patient qualifies for the
	defined discontinued case and at least one has been checked in
Presence/absence of	"reason for discontinuation" of "discontinuation of the survey" of the
reason for	survey form. On the other hand, if a patient qualifies for the defined
discontinuation	discontinued case and no description has been made in the "reason
	for discontinuation" column in the survey form, the case is defined as
	an "unknown/not provided" case.
	It should derive from "reason for discontinuation" of
Reason for	"discontinuation of the survey" of the survey form. Recode the
discontinuation	reason for discontinuation based on other descriptions of "reason for
discontinuation	discontinuation" and "[Humira UC] Conversion data provided for
	analysis". Select "unknown/not provided" for undescribed data".
Reason for	Obtain the detailed items of reason for discontinuation "others" in
discontinuation, other	"[Humira UC] Conversion data provided for analysis".
reasons	
Patients who continue	The patients who are not the discontinued cases are regarded as the

Data name	Derivation and calculation methods
the survey	patients who continue the survey
Presence/absence of	When complication data are contained in the survey form, it should
	be classified as "with complications". When there is no description of
	"presence/absence of complications" in the survey form or the
complications	assessment is impossible, it should be classified as "unknown/not
	provided", and other cases are "no complications".
	When medical-history data are contained in the survey form, it
Presence/absence of	should be classified as "with medical history". When there is no
	description of "presence/absence of medical history" in the survey
medical history	form or the assessment is impossible, it should be classified as
	"unknown/not provided", and other cases are "no medical history".
Complication/Hepatic	When hepatic function disorder data are contained in "171210
function disorder	Complication", it should be classified as "with hepatic function
Tunction disorder	disorder". other cases are "no hepatic function disorder".
Complication/Renal	When renal impairment data are contained in "171210
impairment	Complication", it should be classified as "with renal impairment".
ппрантнени	other cases are "no renal impairment".
Presence/absence of	When circulatory disorder data are contained in "171210
Complication/Circulator	Complication", it should be classified as "with circulatory disorder".
y disorder	other cases are "no circulatory disorder".
Presence/absence of	When blood disorder data are contained in "171210 Complication", it
Complication/Blood	should be classified as "with blood disorder. Other cases are "no
disorder	disorder".
Presence/absence of	When respiratory disorder data are contained in "171210
Complication/Respiratory	Complication", it should be classified as "with respiratory disorder.
disorder	Other cases are "no respiratory disorder".
	If a survey form contains the data other than hepatic function
	disorder, renal impairment, circulatory disorder, blood disorder and
	respiratory disorder, it should be classified as "with other
	complications". Others are "no other complications".
Presence/absence of	
Complication/others	If a survey form contains the data in "171210 Complication" for
	presence/absence of diabetes mellitus, gastrointestinal disorder,
	osteoporosis and malignant tumour as well among the detailed
	classifications of other complications, it should be classified as "with
	complications". Others are "no complications".

Data name	Derivation and calculation methods
	If a survey form contains the data on complications other than
	diabetes mellitus, gastrointestinal disorder, osteoporosis and
	malignant tumour among the detailed classifications of other
	complications, it should be classified as "with other complication of
	other detailed classifications". Others are "no other complication of
	other detailed classifications".
	As for collagen disorder, if "other: collagen disorder" in
	"complications" of "patient information" is checked, it should be
	classified as "with collage disorder. Other cases are "no collagen
	disorder".
Medical history:	When tuberculosis data are contained in "180111 Medical history", it
presence/absence of	should be classified as "with tuberculosis. Other cases are "no
tuberculosis	tuberculosis".
Medical history:	When non-tuberculous mycobacteriosis data are contained in
presence/absence of	"180111 Medical history", it should be classified as "with
non-tuberculous	non-tuberculous mycobacteriosis. Other cases are "no
mycobacteriosis	non-tuberculous mycobacteriosis".
Medical history:	When interstitial pneumonia data are contained in "180111 Medical
presence/absence of	history", it should be classified as "with interstitial pneumonia. Other
interstitial pneumonia	cases are "no interstitial pneumonia".
Medical history:	When bronchitis bacterial data are contained in "180111 Medical
presence/absence of	history", it should be classified as "with bronchitis bacterial. Other
bronchitis bacterial	cases are "no bronchitis bacterial".
Medical history:	When aplastic anaemia data are contained in "180111 Medical
presence/absence of	history", it should be classified as "with aplastic anaemia. Other
aplastic anaemia	cases are "no aplastic anaemia".
Medical history:	When pancytopenia data are contained in "180111 Medical history",
presence/absence of	it should be classified as "with pancytopenia. Other cases are "no
pancytopenia	pancytopenia".
Medical history:	When malignant tumour data are contained in "180111 Medical
presence/absence of	history", it should be classified as "with malignant tumour. Other
malignant tumour	cases are "no malignant tumour".
Medical history:	When medical-history data except tuberculosis, non-tuberculous
presence/absence of	mycobacteriosis, interstitial pneumonia, bronchitis bacterial, aplastic
other medical history	anaemia, pancytopenia and malignant tumour are contained among
other medical history	the medical-history data in the survey form, it should be classified as

Data name	Derivation and calculation methods
	"with other medical history". The remaining cases are "no other
	medical history".
	When "with allergy history in "patient information" of the survey
	form is checked, it should be classified as "with allergy history.
Presence/absence of	When "allergy history unknown" is checked, it should be "unknown"
allergy history	whereas nothing is provided in "presence/absence of allergy history"
	of the form, it should be "not provided". Other cases are "no allergy
	history".
	When "Hepatitis→viral" is selected in "Complications" of "Patient
	information" in the survey form and also "B" is selected for
Patients with an hepatitis	"Hepatitis virus carrier", the patient is classified as a patient with an
B virus infection	hepatitis B virus infection. The patients also include those developed
	an adverse event encoded with the applicable MedDRA PT described
	in "patients with 180111B Hepatitis B virus infection".
	For the items for smoking history in the survey form, when the
	checkboxes of "smoking" or "in the past" are checked, or when "with
	smoking history" is checked and the smoking period is "unknown",
Presence/absence of	both cases should be classified as "with smoking history". When
smoking history	"unknown" is checked for smoking history, it should be "unknown".
	When nothing is described in "presence/absence of smoking history"
	of the survey form, it should be "not provided".
	Other cases are "no smoking history".
	When "smoking" is checked among the items for smoking history in
	the survey form, or when any descriptions are made in the smoking
	period of "smoking", they should be classified as "smoking". When
Detailed classification of	"in the past" is checked or any descriptions are made in the smoking
	period "in the past" in patients who are not classified as "smoking",
smoking history	the case should be classified as "only in the past (not smoking now)".
	When "with smoking" is checked but nothing is checked in the
	detailed classification, or when "unknown" is checked, they should
	be "unknown".
Patients with dosing	Patients other than those who satisfied [1] to [4] of "Administration
deviation of Humira	status (dosage and administration)"
Presence/absence of	When "Self-administration" in the "Administration status of Humira"
self-administration	column is checked at least once, the case should be classified as
	"with" self-administration. Others are "without" self-administration.

Data name	Derivation and calculation methods
	When both "administration by physician" and "self-administration"
	are checked, the case should be "with self-administration".
	When "with" self-administration error is checked in the survey form,
	it should be classified as "with" the error. When "without" is
D / 1 C	checked, it should be "without" the error.
Presence/absence of	When some details are provided along with the onset date in the
self-administration error	self-administration error column irrespective of a check on
	"with"/"without", it should be regarded as "with" the error.
	If nothing is described there, it should be "unknown/not provided".
	It should be identified based on the sex in the patient's information of
G.	the survey form. When multiple items are checked or data without a
Sex	description are included, the case should be classified as
	"unknown/not provided".
	It should be identified based on pregnancy/nursing in the patient's
	information of the survey form. When multiple items are checked or
D / ·	data without a description are included even if the sex has been
Pregnancy/nursing	selected as "woman", the case should be classified as "unknown/not
	provided". If the sex is not "woman" even though a description has
	been made for this item, it is excluded from the calculation.
	It should be identified based on the race in the registration form.
Race	When multiple items are checked or data without a description are
	included, the case should be classified as "unknown/not provided".
	It should be identified based on the year and month of the patient's
	birth or the first administration date of Humira in the survey form.
	For the date of birth, the first day should be imputed to identify it,
	using the following SAS code.
	floor((intck('month', date of birth, the first administration date of
A	Humira) - (day(the first administration date of Humira) < day(date of
Age	birth)))/12)
	Of note, if it is impossible to identify the date of birth or the first
	administration date of Humira due to an incomplete or unknown date,
	select the age provided in the survey form.
	If it cannot be identified based on the date of birth or the age is not
	provided, it is defined as "unknown/not provided".
Pediatrics	Patients aged <15 years
The elderly	Patients aged ≥65 years

Data name	Derivation and calculation methods
Body weight	It should be identified based on the body weight in the patient's
	information of the survey form. When "unknown" is checked or data
	without a description are included, it should be "unknown/not
	provided".
	It should be identified based on the height in the patient's information
Body height	of the survey form. When "unknown" is checked or data without a
	description are included, it should be "unknown/not provided".
BMI	Body weight (kg) / (Body height (cm)/100) ²
	"For XX years and XX months" should be converted into the figure
	in years for "duration of illness" of "patient information" in the
	survey form.
Duration of illness (in	When both figures of year and month: year + month/12
years)	When the figure of year is provided: year
	When the figure of month is provided: month/12
	Other cases are identified as "unknown/not provided" as the duration
	cannot be identified.
	If both "colitis ulcerative" and "others" are checked for indication in
Indication	the survey form, it should be calculated as "colitis ulcerative".
	It should be identified based on "site of disease of colitis ulcerative"
Site of disease	in the survey form. Select "unknown/not provided" for undescribed
	data".
	Conducted: When "HBs antigen test" in the survey form was
	conducted (If "conducted" was not checked but the test results were
IIDa antigan taat	provided, it should be regarded as "conducted")
HBs antigen test	Not conducted: When "HBs antigen test" in the survey form was not
	conducted
	Unknown/not provided: other than the above
